3.4. Rationale for the OPTIFILL clinical trial

Regulatory context:

This OPTIFILL trial is a **pre-CE marking** clinical trial, the aim of which is to evaluate the performance and safety of the PA1704 device in patients for the first time, with a view to its future marketing in Europe and the USA.

Clinical data collected from patients treated with PA1704 will be compared with data collected from the comparator group treated with Bioroot™ RCS. These will also be used by Septodont to feed into the **post-marketing monitoring** plan for the Bioroot™ RCS device.

In order to generate long-term clinical data on the PA1704 MD, as part of the EC marking application filed with the notified body, the sponsor wishes to evaluate the performance and safety of the PA1704 MD for up to 5 years, which is the life span claimed for the BioRoot™ RCS comparator MD.

Objectives:

The aim of this study is to show that the performance and safety of the new filling material are not affected by the change in presentation. To this end, the chosen methodology is a **non-inferiority study of the PA1704 device compared to the BioRoot™ RCS**. The main objective was to assess the **24-month efficacy rate** of endodontic treatment (initial or repeat), determined on the basis of radiological and clinical criteria. Performance and safety at 6 and 12 months are also assessed. The evaluation of the performance and safety PA1704 for up to 5 years has been incorporated into the OPTIFILL study in order to obtain the data needed to monitor the benefit-risk ratio of this new medical device. The OPTIFILL trial is a prospective, randomized, open-label trial with the primary criterion blind. This trial is multicenter and is being conducted in France and in Belgium; the investigators are general dental surgeons and exclusive endodontists.

4. Risks and benefits of the PA1704 investigational device and clinical trial

4.1. Expected clinical benefits of the PA1704 material.

For patients, the expected benefits are linked to treatment:

- Permanent obturation of the root canal(s),
- Preserving the functionality of the filled tooth.

There is no individual benefit linked to patient participation in this trial.

For dental surgeons, the expected benefits of PA1704 are of a practical nature, as the cement is in a ready-to-use format.

4.2. Adverse effects expected from the PA1704 device.

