Retro-alveolar X-rays are taken with an angulator using the parallel planes technique; the **entire tooth should be visible in the image** (crown to apex, passing through the root). There are no other specific settings imposed for the devices.

The images will be converted to .jpg format, without filters, and anonymized before being uploaded to the eCRF.

✓ Procedures for replacing subjects, if necessary.

See Chapter 7.4

6.2. Medical devices under investigation (ready-to-use material PA1704) and comparator (BioRoot™ RCS powder-liquid material)

✓ Comparator Medical Device Description — BioRoot™ RCS:

The selected comparator MD was the BioRoot™ RCS permanent root canal filling material.

BioRoot™ RCS is a Class III implantable medical device for dental use manufactured by Septodont. BioRoot™ RCS is based on Active Biosilicate Technology (ABS). It is a mineral root canal cement composed mainly of tricalcium silicate, zirconium oxide and calcium chloride. It comes in the form of **two products (powder-liquid) that are to be mixed**. Clinical indications, contraindications, characteristics, instructions for use, warnings, storage and disposal procedures are detailed in the instructions for use (see Annexe 3).

Thus, the medical device under investigation (PA1704) and comparator device (BioRoot™ RCS) are 2 calcium silicate-based cements, which are used for the same endodontic indications but come in 2 different forms, as a powder-liquid mixture or as a ready-to-inject paste. The 2 medical devices are similar and the aim of this study is to show that the performance and safety of the new material are not affected by the change in presentation.

✓ Exposure to medical devices under investigation and comparator

Patients included in the study will randomly receive one of 2 filling materials, PA1704 or BioRoot™ RCS, to treat one tooth (one or more root canals depending on the type of tooth affected by pulpal disease). The medical device is administered (implanted) only once, on the day of the endodontic treatment. The material is implanted for the long term, as it is intended to seal the root canals permanently. It is not intended to be removed during the trial, nor after the end of the trial, except where the treatment has failed with an indication to restart treatment.

✓ List of any other medical devices or medicines to be used during the clinical investigation.

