7.3. Degree of significance and power of the clinical trial

The main analysis will be carried out using a one-tailed statistical test with a significance threshold α set at 5%. The clinical trial is designed to ensure 80% power for the main analysis test. Secondary analyses will be carried out using two-tailed statistical tests with a significance threshold α set at 5%.

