7.7. Statistical methods

The statistical methods are based on the following elements and will be detailed in the Statistical Analysis Plan.

7.7.1. Sample description:

The description of the subjects enrolled who completed the trial and those enrolled who left prematurely will be presented using a table of absolute (N) and relative (%) frequency. Reasons for premature discharge and deviations from the protocol will be listed.

7.7.2. Descriptive analyses:

Clinical data collected at enrolment and at each visit will be described. Descriptive statistics will be presented according to the nature of the criterion analyzed:

- Quantitative variable: sample size, number of missing data sets, mean, standard deviation, median, minimum and maximum;
- Qualitative variable: absolute frequencies (N) and relative frequencies (%) per class in each group, number of missing data.

Graphs will be provided for each variable.

7.7.3. Comparative analyses:

A comparison of 2 independent means will be made using the Student's t-test; if the variances are unequal (verified by the Fisher's test), use the Welch's test instead of the Student's test. If the conditions for applying the Student test are not met (n < 30), the non-parametric Wilcoxon test is used.

2 independent percentages are compared using Pearson's Chi-2 test. If the conditions for application are not met (at least one theoretical number < 5), Fisher's exact test is used.

7.7.4. Analysis of primary performance criterion:

As a reminder, the primary performance criterion is the efficacy rate at 24 months of treatment based on clinical criteria assessed by the investigator (tooth functionality and pain level) AND radiological criteria assessed blind by independent reviewers (complete healing, reduction of lesions, failure). In the event of failure at 6 or 12 months, the patient will be considered to have failed at 24 months.

The primary criterion will be analyzed using 2 approaches, in accordance with the literature:

- **Primary analysis of soft criteria**: treatment rates with complete or incomplete cure are compared against failure rates;
- **Secondary analysis of strict criteria**: treatment rates with complete healing are compared against rates of failure or incomplete healing (complete healing can take up to 4 or 5 years).

The comparison of efficacy rates between the 2 groups will be carried out using the Dunnett and Gent χ^2 test (Dunnett CW and Gent M 1977; Elie C et al 2008).

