Maximum pain in the first 7 days and time to onset of maximum pain: Description and comparison, between the PA1704 arm and the BioRoot™ RCS arm, of the maximum pain experienced during the 7 post-operative days and its time to onset by a Student, Welch or Wilcoxon test.

Intra-operative pain relief between T0 and D7: Description of painkiller classes, reasons for use, frequency of use and cumulative dose per patient over 7 days. Description and comparison, between the PA1704 arm and the BioRoot™ RCS arm, of the proportion of patients who used *oral* pain medication between T0 and D7 by Pearson's Chi-2 test or Fisher's exact test.

Description of the surgical technique: Description and comparison, between the PA1704 arm and the BioRoot™ RCS arm, of the type of anesthesia, the technique used to remove the old filling material (if root canal re-treatment only), the technique used to shape the canal, the type of disinfectant and rinse solutions used and irrigation techniques, the method of application of filling material and gutta-percha condensation, and the coronal restoration technique, by Pearson's Chi-squared test or Fisher's exact test. Intraoperative complications will be described where appropriate.

Operator comfort and satisfaction: Description and comparison, between the PA1704 arm and the BioRoot™ RCS arm, of operator comfort criteria. Satisfaction will be described at T0 and 2 years, and the proportions of satisfied operators will be compared.

For the performance criteria (efficacy rate, filling density, and material resorption) evaluated at 3.5 years and 5 years in the PA1704 arm: These criteria will only be described.

7.7.6. Safety/tolerance analysis:

The tolerance analysis will focus on the Tolerance population. Tolerance data is to be expressed as the number of adverse events (AEs) and the number of patients reporting at least one AE. Severity, cause (filling material or surgical technique) and the time of occurrence shall be described. The proportions of AEs and patients with AEs will be compared between the 2 groups. The proportions of patients who used an additional dental consultation for significant post-operative complication or pain will be described and compared, between the PA1704 arm and the BioRoot™ RCS arm, by Pearson's Chi-squared test or Fisher's exact test.

Defects in the devices will be described in the form of a list and proportions will be compared between the 2 groups.

7.7.7. Intermediate analyses:

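### Sections 3.4 and 6.2 promise to show that safety is unaffected by the new presentation, but safety gets only difference tests, with no margin or interval

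*Combined protocol and SAP*

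**What the plan says.** **Aim.** Section 3.4 says the study is to "show that the performance and safety of the new filling material are not affected by the change in presentation", and presents the non-inferiority design as the means of doing so. Section 6.2 repeats it: "the aim of this study is to show that the performance and safety of the new material are not affected by the change in presentation".

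**Where non-inferiority is specified.** Section 5.2 defines the hypotheses for the 2-year efficacy rate. Section 7.2 gives a 13-point tolerance and 66 patients per group (80 after allowance for losses) for that endpoint. Section 7.3 attaches 80% power to the main test, and section 7.7.4 plans a one-sided 95% interval for the efficacy difference.

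**Safety analysis.** In section 7.7.6, "The proportions of AEs and patients with AEs will be compared between the 2 groups". For consultations, "The proportions of patients who used an additional dental consultation for significant post-operative complication or pain will be described and compared", by Pearson's or Fisher's test. For defects, "Defects in the devices will be described in the form of a list and proportions will be compared between the 2 groups". The general rule in section 7.7.3 is that "2 independent percentages are compared using Pearson's Chi-2 test", with Fisher's exact test if an expected count is below 5. On the error rate, section 7.3 states: "Secondary analyses will be carried out using two-tailed statistical tests with a significance threshold" of 5%.

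**Not given for safety.** There is no margin, confidence interval, power or expected AE rate. Sections 4.2 and 14.4 say that the device's adverse effects are not known.

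**The concern.** A claim that something is unaffected needs an analysis that can rule out an important effect. The plan supplies one for efficacy but not for safety. The only inferential output planned under section 7.7.6 is a p-value for a difference. If it exceeds 0.05, the data may still be compatible with a sizeable excess of harm on PA1704, and without an interval the reader cannot see how large.

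This matters because section 3.3 describes the trial as the first use of PA1704 in humans, and section 3.4 says the results will support a marketing application. A report of no significant difference in AEs, set beside the aim in sections 3.4 and 6.2, would invite a conclusion that the analysis cannot carry.

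**Working it through.** **1. The plan's own sample size.** Inputs from sections 7.2 and 7.3: 90% efficacy in both arms, margin 0.13, one-sided 5%, power 80%.

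n = (1.645 + 0.842)² × 2 × 0.90 × 0.10 / 0.13² = 65.9, so 66 per group, as stated. Then 66 × 1.2 = 79.2, rounded to 80. The size is therefore set entirely by the efficacy endpoint.

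**2. Inputs for the safety comparison.**
- 80 treated patients per arm (section 6.2), analysed as the Tolerance population (section 7.6).
- Two-sided 5% (section 7.3).
- Pearson chi-square, or Fisher's exact test if an expected count is below 5 (section 7.7.3).
- Comparator rate of patients with at least one AE: not given, so assumed to lie between 5% and 30%.

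**3. Power under the planned rule.** Every pair of counts (x₁ on PA1704, x₀ on BioRoot RCS) is enumerated. Power is the sum of Bin(x₁; 80, p₁) × Bin(x₀; 80, p₀) over the tables with p < 0.05 and a higher rate on PA1704.

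| Comparator rate | Doubled rate | Power, 80 per arm | Power, 66 per arm |
|---|---|---|---|
| 5% | 10% | 20% | 17% |
| 10% | 20% | 42% | 36% |
| 15% | 30% | 64% | 55% |
| 20% | 40% | 80% | 72% |
| 25% | 50% | 91% | 86% |
| 30% | 60% | 97% | 94% |

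Check of the 10% v 20% row with 80 per arm, by normal approximation: (0.10 - 1.96 × √(2 × 0.15 × 0.85/80)) / √((0.09 + 0.16)/80) = (0.1000 - 0.1107)/0.0559 = -0.19, which gives 42%. By the same approximation, power for a doubling passes 50% at a comparator rate of 11.8% with 80 per arm, or 13.8% with 66.

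For a fixed 10-point excess the pattern reverses, because the variance grows with the rate:

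| Rates | Power, 80 per arm | Chance of missing it |
|---|---|---|
| 5% v 15% | 57% | 43% |
| 10% v 20% | 42% | 58% |
| 20% v 30% | 31% | 69% |
| 30% v 40% | 27% | 73% |

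**4. What a non-significant result can hide.** Take 16/80 on PA1704 and 8/80 on BioRoot RCS. The pooled rate is 24/160 = 0.15, and z = 0.10/√(0.15 × 0.85 × 2/80) = 0.10/0.0565 = 1.77, so p = 0.077.

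The Wilson limits are 12.7% to 30.0% for 16/80 and 5.2% to 18.5% for 8/80. The Newcombe 95% interval for the difference is:
- lower limit: 0.10 - √((0.200 - 0.127)² + (0.185 - 0.100)²) = -1.2 points;
- upper limit: 0.10 + √((0.300 - 0.200)² + (0.100 - 0.052)²) = +21.2 points (computed from unrounded limits).

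Even 8/80 v 8/80 gives -9.8 to +9.8 points.

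**5. Expected precision.** With equal rates and 80 per arm, the approximate 95% half-width is 1.96 × √(2p(1 - p)/80): 6.8, 9.3, 11.1, 12.4 and 14.2 points at p = 5%, 10%, 15%, 20% and 30%.

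**The case against.** **No rule reads non-significance as safety shown.** The formal objective in section 5.1 is to evaluate adverse events, and sections 5.2 and 7.7.8 tie the non-inferiority conclusion to 2-year efficacy. The no-difference wording for safety sits in the rationale and the device description. This is correct: the misreading is possible, not planned. But it leaves sections 3.4 and 6.2 promising something that sections 5.1, 5.2 and 7.7.6 do not deliver.

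**The test might detect a doubling.** A reader might infer that a trial of this size would usually miss a doubling of patients with AEs. The documents do not support that. It is true only if the comparator rate is below about 12% (about 14% with 66 per arm), and no rate is given. Under sections 14.1 and 14.2.1 all AEs count, whether or not related to the device, including those from the procedure, and section 14 has them actively sought, so a higher rate is plausible. Nor can one say that any important excess would more often than not be missed: a rise from 5% to 15% is detected 57% of the time.

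**Patients with AEs are not the only comparison bearing on safety.** Consultations and defects are compared in section 7.7.6, and pain and oral painkiller use in section 7.7.5. Severity, cause and timing of AEs are also described. This stands, but these comparisons are also difference tests without a margin or interval.

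**Detail is left to a later Statistical Analysis Plan.** Section 7.7 says so, and that plan could add intervals. Their absence can be asserted only for this document. However, section 7.7 says the later plan will detail the methods listed here, which for safety are difference tests, and it cannot by itself correct the aim stated in the protocol.

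**Conclusion.** The mismatch is real: the aim covers safety, and the method able to support it covers only 24-month efficacy. The planned tests are valid as tests of difference, but a non-significant result from them would not show that safety is unaffected, whatever the AE rate.

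How weak the tests are depends on a rate that the documents do not give. Over assumed comparator rates of 5% to 20%, power for a doubling runs from about 20% to 80%. Over 5% to 30%, power for a 10-point excess runs from 57% down to 27%. These figures assume that all 80 patients per arm are treated and observed; losses would lower them.

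The primary efficacy conclusion is untouched. This is an inexpensive improvement to the safety analysis and to the wording of the aim.

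**What to change.** - **Section 7.7.6, estimation.** For the patient-level proportions already planned (at least one AE; at least one additional consultation), report the PA1704 minus BioRoot RCS difference with a two-sided 95% confidence interval, for example Newcombe's.
- **Section 7.7.6, time window.** State that the comparison covers the common 24 months. Section 5.1 collects AEs to 5 years in the PA1704 arm only. Section 7.7.7 makes the later analyses non-comparative, but section 7.7.6 sets no window.
- **Section 7.7.6, interpretation.** Add a sentence such as: *A non-significant difference will not be interpreted as showing that safety is unaffected; the upper confidence limit is the largest excess not excluded.*
- **Sections 3.4 and 6.2.** Limit the no-difference (non-inferiority) aim to 24-month efficacy and describe safety as estimated, in line with sections 5.1 and 5.2.

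The cost is wording in three sections and two intervals from data already collected, with no extra patients or visits. The drawback is a more modest safety claim, since the intervals will be wide: roughly ±7 to ±14 points over the assumed rates.

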7.4. Expected drop-out rates

The study includes a 24-month follow-up for patients in the BioRoot RCS arm, and a 5-year follow-up for patients in the PA1704 arm, which may mean that some patients will withdraw or be dropped from the study. These patients will not be replaced. The calculation of the number of subjects to be enrolled allowed for a 20% increase in this number, in order to anticipate the drop-out rate at 2 years.

7.5. Procedures for taking all data into account:

Data review and database freezing: Before each statistical analysis (intermediate and final), a data review meeting will be held, attended by *at least* the sponsor and the CRO's biostatistician in charge of the statistical analysis. This will enable deviations from the protocol to be identified and categorized, so that samples of patients can be evaluated for statistical analysis. This will provide an opportunity to identify factors not initially considered that could influence the trial results and which would be worth taking into account in the analysis. At the end of the last data review meeting, the clinical database will be frozen.

Once the clinical database has been frozen, statistical analyses will be carried out by the CRO in accordance with the trial's Statistical Analysis Plan.

7.6. Definition of analysis populations:

The Tolerance population is the entire population treated with the investigational MD or the comparator MD. Patients will be analyzed according to the medical device they actually received (if a patient is randomized to one arm but receives the medical device from the other arm (allocation error), they will be analyzed according to the medical device they actually received).

The modified ITT (mITT) population is the set of patients included in the clinical trial, meeting the major eligibility criteria (see below), having been treated with one of the MDs, and for whom at least one set of performance data is available (efficacy at 6 months, 12 months or 24 months based on clinical and radiological criteria). Evaluation of breaches of the eligibility criteria will be carried out blind to whichever medical device was allocated and to post-randomization data. Patients will be analyzed according to the intention-to-treat principle, i.e. according to the medical device for which they have been randomized.

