No interim analysis of the primary criterion is planned. The main analysis will only be carried out after the 2-year follow-up of all patients enrolled.

Two interim analyses of the secondary criteria have been planned. These will be carried out after 6 and 12 months' follow-up for all included patients.

The alpha risk will not be inflated, as the main criterion will not be analyzed in the interim analyses. Therefore, no alpha risk adjustment method is required. The final analysis will focus on the primary and secondary criteria.

For patients treated with the PA1704 ready-to-use filling material and who agree to be followed-up with for up to 5 years, a non-comparative descriptive analysis of secondary performance and safety criteria at 3.5 years and 5 years will be carried out at the end of their participation.

7.7.8. Criteria for stopping the clinical trial from a statistical point of view:

None. Interim analyses are only used to collect data on secondary criteria before the end of the study. The conclusion on the non-inferiority of PA1704 compared to BioRoot™ RCS will only be made on the final analysis at 2 years.

7.7.9. Changes to the statistical analysis plan:

The statistical analysis plan will be drawn up before the first interim analysis is carried out. The initial analysis strategy may undergo minor modifications following each data review, and the new statistical analysis plan will be described in detail at that time.

7.7.10. Specification of sub-groups for further analysis:

The following sub-group analyses will be carried out, at least on the PP population, during the final analysis at 2 years. Other factors not considered in this protocol may be added in the Statistical Analysis Plan.

- For the primary criterion, the rate of effective treatment at 2 years:
 - Prognostic factors at enrolment
 - Presence or absence of a periapical lesion,
 - Indication for endodontic treatment: initial versus repeat endodontic treatment,
 - Factors related to the surgical procedure
 - Type of rinse solution used to finalize root canal disinfection,
 - Operating techniques used: technical platform used (whether or not a microscope was used), manual files versus continuous rotation versus alternative rotation.
- Post-operative pain:
 - Operating techniques used: manual files versus continuous rotation versus alternative rotation.
 - Initial pulp pathology (pre-existing inflammatory situation or necrosis or live pulp),

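### Section 7.7.9 does not shield the primary analysis from changes made after the 6- and 12-month comparisons by arm, whose failures count in the 24-month endpoint

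*Combined protocol and SAP*

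**What the plan says.** **Timing.** Under section 7.7.9, "The statistical analysis plan will be drawn up before the first interim analysis is carried out". The permission to change follows at once: "The initial analysis strategy may undergo minor modifications following each data review". 'Minor' is not defined, and no analysis is excluded. Section 7.5 sets the rhythm: "Before each statistical analysis (intermediate and final), a data review meeting will be held". At least the sponsor and the CRO biostatistician in charge of the analysis attend. Each review is also meant to "identify factors not initially considered that could influence the trial results and which would be worth taking into account in the analysis".

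**Interim content.** Section 7.7.7 plans two interim analyses of the secondary criteria: "These will be carried out after 6 and 12 months' follow-up for all included patients". Section 7.7.5 lists the 6- and 12-month efficacy rates among these criteria and compares them between arms by chi-square or Fisher's exact test.

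**Link to the primary criterion.** Section 7.7.4 states: "In the event of failure at 6 or 12 months, the patient will be considered to have failed at 24 months". Sections 6.5.2 and 7.7.11 carry failures forward in the same way.

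**Error control.** Section 7.7.7 reasons: "The alpha risk will not be inflated, as the main criterion will not be analyzed in the interim analyses". Section 14.6 records that no data monitoring committee applies. No text limits who sees the interim results by arm.

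**The concern.** The 6- and 12-month comparisons are labelled secondary, but every failure in them is already a settled 24-month failure. They therefore show part of the primary result by arm. The same people may then revise the analysis strategy before the primary analysis is run.

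The risk is not repeated testing. It is that a detail of the primary analysis could be settled, or resettled, by people who know which choice favours which arm. In a non-inferiority trial intended for a CE-marking application, that would weaken the claim even if every change were made in good faith, because the sponsor could not show that the choice was independent of the results.

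**Working it through.** **1. Order of events** (sections 7.5, 7.7.5, 7.7.7, 7.7.9)

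| Step | By-arm efficacy comparison already made |
|---|---|
| First SAP; data review 1 | none |
| 6-month analysis by arm | – |
| Data review 2 | 6 months |
| 12-month analysis by arm | – |
| Data review 3 | 6 and 12 months |
| Primary analysis at 24 months | – |

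Two of the three reviews follow a between-arm comparison, including the one directly before the primary analysis.

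**2. What is still open in the primary endpoint**

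- *Soft criterion.* Section 6.1 counts effective or uncertain treatment as success. Section 7.7.4 counts complete or incomplete cure as success, against failure. In Table 4 a stable lesion in an asymptomatic, functional tooth is uncertain. That is a success under section 6.1, but under section 7.7.4 it is neither a complete nor an incomplete cure.
- *Table 4.* No row covers a tooth with no lesion at follow-up that is symptomatic, whether or not a lesion was present at T0.

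Either gap could be closed later as a minor clarification.

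**3. The plan's own sample size**

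Inputs from sections 7.2 and 7.3: 90% efficacy in both arms, 13-point margin, one-sided 5%, 80% power.

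n = 2 × 0.90 × 0.10 × (1.645 + 0.842)² / 0.13² = 65.85, so 66 per group, as stated.

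**4. What one patient is worth**

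One patient in 66 is 1/66 = 1.5 points. Take 59/66 successes with BioRoot RCS (89.4%) and the unpooled one-sided 95% lower limit:

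- PA1704 57/66: difference −3.0 points; standard error √(0.8636 × 0.1364/66 + 0.8939 × 0.1061/66) = 0.0568; lower limit −3.0 − 1.645 × 5.68 = −12.4. Non-inferior.
- PA1704 56/66: difference −4.5 points; standard error 0.0582; lower limit −4.5 − 1.645 × 5.82 = −14.1. Not shown.

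The constrained-variance z values are 1.79 and 1.48 against 1.645, so the conclusions are the same. Near the margin, the third net failure decides the trial.

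**5. How much is visible by 12 months (assumed shares)**

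The documents do not say what share of failures occurs early. With 24-month failure b = 0.10 (6.6 per 66) and 12-month failure a, the patient-level correlation is √[a(1 − b) / ((1 − a)b)].

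| Share of failures by 12 months | a | Expected per 66 | Correlation |
|---|---|---|---|
| 25% | 0.025 | 1.7 | 0.48 |
| 50% | 0.05 | 3.3 | 0.69 |
| 75% | 0.075 | 5.0 | 0.85 |

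**6. Hypothetical effect on the error rate**

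- *Scenario A.* True rates are at the null boundary (90% versus 77%), 66 per arm, constrained-variance test, 400,000 replicates. A group of 10% or 20% of patients is dropped if PA1704 has more early failures in it. One-sided error is 6.5% to 7.8%. The same test with a fixed choice gives 5.8% to 6.2%, so the increment over analysing everyone is 0.7 to 2.0 points (6.52 − 5.79; 7.84 − 5.82).
- *Scenario B.* One of k candidate primary analyses, mutually correlated 0.8 to 0.9, is picked on its 12-month result, with a 12- to 24-month correlation of 0.69 to 0.94. Error is about 6% to 7.5% for k = 2 and about 7.5% to 10% for k = 4.

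**The case against.** The strongest reply is that the primary analysis is already in the protocol. Section 5.2 gives the hypotheses, 7.2 the margin, 7.3 the one-sided 5% level, 7.6 the populations and 7.7.4 the test, and section 7.7 makes the per-protocol population the main one. Replacing any of these would naturally be a protocol change under section 9, which goes to ethics committees and authorities. This largely stands. It does not close the gap, because section 9 neither defines a substantial change nor mentions the SAP, and the open classifications in step 2 could be settled without touching any of those items.

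Second, section 7.6 has eligibility breaches and major deviations judged blind to device and to post-randomization data. That protects the classification of individual cases. It does not expressly cover rewriting the rules or the endpoint definition, and the patient identifier in section 6.6.4 contains the arm.

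Three stronger readings are tempting but not supported:

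- *That the statement on alpha in 7.7.7 is wrong.* It is correct about repeated testing: there is no interim primary test and no stopping rule, and the conclusion comes only at 2 years. It is silent on result-dependent changes.
- *That every data review takes place with by-arm results known.* Review 1 precedes the first comparison, and the first SAP also predates it.
- *That new covariates could alter the primary test.* The test is an unadjusted comparison of two proportions. Section 7.7.10 puts added factors under subgroup analyses, and section 7.5 does not say that they enter the primary test.

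Section 7.7 also defers detail to an SAP whose fuller text is not in the documents. It may define 'minor'; that cannot be checked.

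**Conclusion.** The point holds in limited form. After the 6- and 12-month comparisons by arm, section 7.7.9 leaves room to modify the analysis strategy without excluding the primary analysis, while parts of the primary endpoint definition remain unsettled. The main elements of the analysis are already fixed, so the exposure lies in details rather than in the whole analysis.

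Its size cannot be established from the documents. The range of roughly 6.5% to 10% against a nominal 5% is a hypothetical illustration. It depends on assumed early-failure shares, an assumed group of patients or number of alternative analyses, and deliberate selection. A reader might take it as the trial's actual error rate, but nothing in the documents shows several interchangeable primary analyses or an intention to choose among them. Part of the excess in scenario A is the small-sample behaviour of the test itself. What follows from the planned sample size alone is that near the margin one net reclassification can change the conclusion. That is enough to justify a correction costing only wording.

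**What to change.** **Section 7.7.9.** State that the primary endpoint definition, the per-protocol and mITT rules, the test and the margin are final in the SAP version signed before the 6-month by-arm analysis, and cannot be modified after it. That version should reconcile the soft criterion in sections 6.1 and 7.7.4 and assign an outcome to every combination missing from Table 4. Later changes may concern only secondary or exploratory analyses, including added subgroup factors, and are reported as post hoc.

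**Section 7.7.7.** Add that the error rate is preserved because there is no interim primary test or stopping rule and because the primary analysis is locked.

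**Cost.** Protocol and SAP wording, and less freedom to amend the SAP later. Sample size, visits and the interim analyses are unchanged.
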